Although short-term opioids can be effective to manage moderate to severe pain, they are associated with a variety of opioid related adverse events (ORAEs), including potentially incapacitating side effects and serious adverse events. For postsurgical pain, patients are at greatest risk for ORAEs during the first 24 hours after surgery when their opioid use is highest [11]. The use of opioids to manage postsurgical pain may be of particular concern for spine surgery, since many patients are already using opioids prior to their surgical procedure. This increases the possibility of ORAEs with higher perioperative doses and continued use beyond the perioperative period [3]. In addition, consumption of opioids is often an outcome measure in spine surgery, and continued or increased use is considered an indicator that the surgical procedure was not successful [12]. It may therefore be beneficial to minimize the amount of opioids consumed for postsurgical pain.

Given the limitations of current approaches to managing postsurgical pain, as well as the consequences of not adequately managing pain following surgical procedures, researchers are continually developing and investigating new approaches that provide optimal pain management. Postsurgical pain management regimens are also being evaluated and refined as a component of broader enhanced recovery after surgery (ERAS) initiatives intended to improve outcomes, reduce hospital LOS, and promote return to normal activities following elective surgical procedures [13]. These initiatives generally favor approaches to manage postsurgical pain that may increase early ambulation and discharge (e.g. regional or local analgesia with local anesthetics) while discouraging those that may decrease them (e.g. IV PCA with opioids).

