- 5. Reduced time to achieve physical therapy discharge criteria (criteria set according to each patient's living situation, preoperative physical function, comorbidities, and other goals)
- 6. Reduced inpatient length of stay (LOS)

Study Benefits to Virtua

This study could potentially benefit Virtua in several ways. If Exparel is shown to reduce postoperative pain for spine surgery patients, and consequently reduce their opioid consumption for postoperative pain management, then there could be the potential to see an improvement in patient satisfaction with regards to pain management. In addition, Virtua could stand to gain some cost savings if Exparel is shown to support decreased incidence of ORAEs such as respiratory depression, leading to reduced time to physical therapy discharge criteria and consequently reduced LOS.

If on the other hand, the study indicates that the more expensive Exparel is no more effective at managing postoperative pain compared to the cheaper alternatives, then Virtua stands to directly gain significant cost savings by adopting the use of the cheaper options as standard practice.

Study Methodology

Patients who meet all of the following inclusion criteria may be eligible to participate in the study if:

- 1. Age 18 or older;
- 2. Primary indication is low back pain, lumbosacral radiculopathy, lumbar disc degeneration, lumbar disc herniation, stenosis, spondylolisthesis, spondylolysis, or deformity requiring surgical intervention;
- 3. Scheduled to undergo primary, 1 or 2 level, posterior lumbar laminectomy with or without fusion, discectomy with fusion, or fusion at Virtua Memorial Hospital;
- 4. Willing to provide informed consent, participate in study, and comply with study protocol.

Patients who meet any of the following criteria may not be eligible to participate:

- 1. Hypersensitivity or allergy to local anesthetics;
- 2. Pregnant or contemplating pregnancy prior to surgery;
- 3. Previous surgery in lumbar spine (i.e. other than microdiscectomy);
- 4. Prior treatment for alcohol, recreational drug, or opioid abuse;
- 5. Serious spinal conditions (e.g. spinal cord compression, cauda equina syndrome, spinal infection, spinal tumor, spinal fracture, inflammatory or systemic spinal arthritis);
- 6. Surgery involving more than 2 vertebral levels;

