- 7. Worker's compensation or personal injury related to lumbar spine (treatment outcomes may be affected by patient's personal interests [21]; could also run into potential issues with reimbursement).
- 8. Lactating women
- 9. Patients with end stage liver disease

During the preoperative office visit, the surgeon will inform patients that appear to meet study eligibility criteria, about the study, and discuss the differences between the three postoperative pain management alternatives, including their potential risks and benefits. The surgeon will make clear to the patient that consenting to be a part of the study means that the patient has agreed to be randomly assigned to one of the three postoperative pain management groups. The patient would be told that the random assignment is going to be determined by rolling a standard die. The patient would be informed that the patient's pain would be controlled regardless of group assignment and that no placebos would be used.

Patients who agree to learn more about the study will be approached by a designated and trained study physician assistant (PA), briefly informed about the study, and asked if they wish to complete the screening questionnaire (Appendix 1) to see if they may be eligible to participate. Once the screening questionnaire is completed by the patient, it will be reviewed by the PA to ask any required clarifying questions and obtain additional information to determine eligibility. Participants who appear to meet eligibility criteria will be reviewed by the PA with one of the study investigators prior to confirming if they are eligible to enroll in the study.

Patients who are deemed eligible to participate in the study and are willing to participate will be asked by the PA to complete the research informed consent. This document will be summarized verbally by the PA and potential participants will be given the opportunity to ask questions about the protocol or their involvement prior to providing consent. Those who agree to participate and provide research informed consent will be enrolled in the study, and given a copy of the research informed consent document. The patient's informed consent would be added to the patient's chart.

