Secondary outcome measures in this study include total opioid consumption. All opioid analgesics used in the hospital will be recorded in the participant's clinical record, including: Name of medication (e.g. morphine); Dose administered (e.g. 10mg); Route of administration (e.g. IV, IM, oral); Reason for administration (e.g. surgical site pain). All opioid analgesics will be converted into oral mg morphine equivalent to determine the total dose of opioids used during the hospital stay using the conversion factors in Appendix 2. Other secondary outcome measures include mean time to achieve physical therapy discharge criteria, mean LOS, and incidence of ORAEs. ORAEs will be documented using the checklist shown in Appendix 3 with assistance from a nurse during every nursing shift (i.e. every 12 hours) until hospital discharge).

Means will be compared among all the three arms using analysis of variance, proportions will be compared using chi-square tests, and logistic regression will be used to analyze for confounding effects. All statistical analyses will be conducted in Minitab 16 Statistical Software.

Protection of Human Subjects

Throughout the study, the principal investigators (Virtua Memorial spine surgeons and PAs), will be the only ones with access to the data collection database. Following the completion of the study, all personal health information collected, including name, gender, age, significant medical comorbidities, and postoperative complications, will be de-identified as soon as possible prior to data analysis and any subsequent publications or research submissions. Patient would be told participation is purely voluntary with no monetary reimbursement and minimal risk of being assigned to one of the three pain management groups.

References

- 1. Centers for Disease Control and Prevention (CDC). National Hospital Discharge Survey: 2006 Annual Summary. Vital and Health Statistics, 2010;13(168).
- 2. Centers for Disease Control and Prevention (CDC), Health, United States, 2012: With Special Features on Emergency Care. 2012: Hyattsville, MD.

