APPENDIX 1. SCREENING QUESTIONNAIRE

Participant information

Last name	Date of birth	//
First name	Age	

Contact information

Home phone	() -	Cell phone () -
Home street address		
Home city, state, Zip		
Email		

Inclusion criteria

#		Yes	No
1	Are you able to speak, read, and write in English?		
2	Are you able to speak, read, and write in Spanish?		
3	Do you have low back pain, radiculopathy, disc degeneration, disc		
	herniation, stenosis, spondylolisthesis, or mild deformity?		
4	Are you scheduled for lumbar spine surgery at Virtua Memorial Hospital		
	in the next 30 days?		
5	Are you willing to participate in the study and comply with the study		
	protocol?		

Exclusion criteria

#	Question	Feet	Inches
1	What is your current height?		
2	2 What is your current weight?		
		Yes	No
3	Have you ever been diagnosed with a mental health conditions such as anxiety or depression?		
4	Are you currently taking medication for depression, anxiety, or any other mental health condition (e.g. Prozac, Xanax, Ativan, Zoloft)?		
5	Have you ever been treated for alcohol, recreational drug, or narcotic medication abuse?		
6	Have you ever had an allergic reaction to any type of local anesthetic such as lidocaine, procaine, or Marcaine®?		
7	Have you ever had spinal fusion surgery (e.g. rods, screws, cages, implants) before?		
8	Have you been taking opioid analgesics (also known as narcotics) such as Vicodin, Percocet, or OxyContin for more than 30 days?		
	Females only:	Yes	No
9	If you are female are you currently pregnant, or do you plan on becoming pregnant before your surgery?		

Pain diagram

Instructions

Please indicate where you currently have pain in your body.

Please use the marks below to indicate each type of symptom you may have.

ACHE	NUMBNESS	PINS & NEEDLES	BURNING	STABBING
$\land \land \land \land$	0000	====	XXXX	////
$\land \land \land \land$	0000	====	XXXX	////

Pain medication questionnaire

Instructions

Please indicate if you have taken any of the following medications for pain in the past month:

Brand name	Generic name	Yes	No
Actiq	Fentanyl transmucosal		
Advil	Ibuprofen		
Aleve	Naproxen		
Avinza	Morphine extended-release		
Bayer	Aspirin		
Butrans	Buprenorphine transdermal		
Celebrex	Celecoxib		
Codeine	Codeine		
Darvocet	Dextropropoxyphene		
Darvon	Propoxyphene		
Demerol	Meperidine		
Dilaudid	Hydromorphone		
Dolophine	Methadone		
Duragesic	Fentanyl transdermal		
Embeda	Morphine / naltrexone extended release		
Exalgo	Hydromorphone extended release		

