APPENDIX 2. CONVERSION FACTORS FOR COMMON OPIOID ANALGESICS TO ORAL MORPHINE EQUIVALENTS

Drug	Route	*Approximate Equianalgesic	**Morphine Equivalent
		Dose (mg)	Dose (MED) Factor
Codeine	Oral	200	0.15
Fentanyl	Parenteral	0.1	300
Hydrocodone	Oral	30	1.00
Hydromorphone	IM	1.5	20
Hydromorphone	Oral	7.5	4
Morphine	IM/IV	10	3
Morphine	Oral	30	1
Oxycodone	Oral	20	1.5
Oxymorphone	IM	1	30
Methadone	Oral	7.5	4

* Equivalent to 30 mg of oral morphine (Source: http://www.globalrph.com/narcotic.htm)

** 1mg of the drug converted to equivalent mg of oral morphine

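### Preoperative opioid use is recorded without dose or frequency and no covariate adjustment is planned, which costs precision on the opioid outcome

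*Combined protocol and SAP*

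**What the plan says.** **Prior use is expected to matter.** The Background states that "many patients are already using opioids prior to their surgical procedure". It also describes opioid-induced hyperalgesia as a way in which preoperative use prolongs and increases pain.

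**Eligibility.** The exclusion list in Study Methodology has one opioid-related entry, "Prior treatment for alcohol, recreational drug, or opioid abuse". It does not mention current prescribed use and sets no washout. The exclusion section of the Appendix 1 form, however, contains item 8: "Have you been taking opioid analgesics (also known as narcotics) such as Vicodin, Percocet, or OxyContin for more than 30 days"? The physician assistant reviews the form and may "ask any required clarifying questions and obtain additional information to determine eligibility".

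**Baseline record.** The pain medication questionnaire in Appendix 1 opens with "Please indicate if you have taken any of the following medications for pain in the past month" and offers yes or no for each named product. It has no field for dose, frequency or duration.

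**Outcome.** Study Methodology states: "All opioid analgesics will be converted into oral mg morphine equivalent to determine the total dose of opioids used during the hospital stay". The drug, dose, route and reason for each administration are recorded, but the total is not limited to any reason and no home dose is subtracted.

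**Analysis.** Means are compared across the three arms by analysis of variance. Confounding is left to logistic regression, and no covariates are named.

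**The concern.** The plan itself names prior opioid use as common and as a driver of pain, but does not measure how much each patient takes. Two patients who tick the same product row look the same on that row whether they took it once in the month or every day. If home opioids are continued in hospital, they enter the outcome together with opioids given for surgical pain.

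Prior daily dose is a plausible strong predictor of total in-hospital opioids, and probably of pain scores. Left out of the model, it stays in the error term and widens the confidence interval for every between-arm difference. Opioid consumption is the second hypothesis, the first-named secondary outcome and part of the stated benefit to the institution. Dose has to be collected at baseline; it is hard to reconstruct reliably afterwards.

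**Working it through.** **1. The plan's own figure.** Inputs from Study Methodology: a 1-point difference, variance 2, three groups, 80% power, significance level 0.05. With means 0, 0.5 and 1, the noncentrality is n × Σ(mean − grand mean)² / variance = 40 × 0.5 / 2 = 10, and the F test has 80.5% power. So 40 per group reproduces; 45 per group gives 85.2%. This calculation is for pain. The documents give no sample size or power for opioid consumption.

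**2. What the form can and cannot separate.** Codeine and the extended-release products have separate rows, and item 8 separates use beyond 30 days. The form therefore supports coarse adjustment by any use, drug, formulation and duration over or under 30 days. It cannot separate low from high dose, or occasional from daily use, within a product.

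**3. Precision lost.** Let r be the within-arm correlation between preoperative daily dose and in-hospital total. The documents do not give it; I assume 0.3 to 0.6. Adjustment leaves a fraction 1 − r² of the variance.

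- Unadjusted sample size matching 40 with full dose adjustment: 40 / (1 − r²).
- Coarsely adjusted sample size matching 40 with full dose adjustment, if the yes/no data capture half of r² (a second assumption): 40 × (1 − r²/2) / (1 − r²).

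| r | r² | versus no adjustment | versus coarse adjustment |
|---|---|---|---|
| 0.3 | 0.09 | 40/0.91 = 44 | 40 × 0.955/0.91 = 42 |
| 0.5 | 0.25 | 40/0.75 = 53 | 40 × 0.875/0.75 = 47 |
| 0.6 | 0.36 | 40/0.64 = 62.5 | 40 × 0.82/0.64 = 51 |

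**4. The same loss as power.** Take a two-arm comparison with 40 per arm, two-sided 0.05, that would have 80% power with full dose adjustment. The detectable difference is (1.96 + 0.84) × √(2/40) = 0.63 adjusted SD. Without adjustment, power is Φ(2.80 × √(1 − R²) − 1.96). With coarse adjustment capturing half of R², the root becomes √((1 − R²)/(1 − R²/2)).

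| R² (assumed) | no adjustment | coarse adjustment |
|---|---|---|
| 0.1 | 76% | 78% |
| 0.2 | 71% | 75% |
| 0.3 | 65% | 72% |
| 0.4 | 58% | 68% |
| 0.5 | 51% | 63% |

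**5. Chance imbalance.** If 40% of enrollees are prior users (assumed), the standard error of the difference in that share between two arms of 40 is √(2 × 0.4 × 0.6 / 40) = 0.11, or 11 percentage points. For 20% to 50% it is 9 to 11 points. The die roll is not stratified, so the design does not limit this.

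**6. Conversion table.** Appendix 2 is headed "CONVERSION FACTORS FOR COMMON OPIOID ANALGESICS TO ORAL MORPHINE EQUIVALENTS". Against the opioids in Appendix 1, it has no row for tramadol, tapentadol, meperidine, levorphanol, buprenorphine or propoxyphene, nor for transdermal or transmucosal fentanyl. Oxymorphone has only an IM row, and Appendix 1 gives no route for it.

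**The case against.** A reader might infer that regular opioid users are plainly eligible, because the protocol excludes only past treatment for abuse. The documents do not settle this. Item 8 sits in the form's exclusion section, and the form is reviewed for eligibility. On the other side, that section also holds height, weight and mental-health items that are not in the protocol's list, so the position of item 8 does not by itself make it a criterion. The supportable statement is that the two texts disagree on use beyond 30 days. Users of 30 days or less are eligible on either reading.

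A reader might also infer that the opioid comparison cannot be adjusted, or that it is confounded. Neither follows. Coarse adjustment is available from the form, and the recorded reason for administration could support a sensitivity analysis limited to surgical-site pain. Assignment is random, so prior dose is balanced in expectation, and the error rate of the unadjusted ANOVA already allows for chance imbalance.

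Nor do the gaps in Appendix 2 show that the outcome cannot be computed. Appendix 1 lists home drugs, while Appendix 2 converts opioids given in hospital. A missing row affects the planned total only if such a drug is given there.

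Finally, the size of the gain rests on assumed correlations, and it would shrink if long-term users turn out to be excluded. All of this stands, and it limits the point. It does not supply a dose field, a named covariate or a suitable model for a continuous total.

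**Conclusion.** The point holds as a precision problem that is cheap to correct. Prior daily dose is not collected, so it cannot be adjusted for. The coarser adjustment that the form would allow is not planned, and logistic regression is the wrong model for a continuous total. Under r = 0.3 to 0.6, full dose adjustment is worth about 44 to 62 patients per group for 40 when set against the planned unadjusted analysis. Set against coarse adjustment that captures half the explained variance, it is worth about 42 to 51. Both ranges rest on assumptions, and the 40 is borrowed from the pain calculation. Systematic bias between arms is not shown.

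Two related defects need no assumption: item 8 has no counterpart in the protocol's exclusion list, and Appendix 2 lacks factors for several opioids and routes named in Appendix 1.

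**What to change.** 1. Add usual dose and times per day to the opioid rows of the Appendix 1 medication questionnaire, completed before the die roll. Convert them to oral morphine equivalents per day, with non-users set to zero.
2. Prespecify a linear model (ANCOVA) for total opioid consumption, and for mean pain score, with treatment arm and preoperative daily dose as terms. Do not use logistic regression for these continuous outcomes.
3. Reconcile item 8 of the form with the exclusion list in Study Methodology, so that the status of patients using opioids for more than 30 days is stated once and consistently.
4. Before enrolment, extend Appendix 2 to every opioid and route in Appendix 1, so that home doses, and any such drug given in hospital, are converted by a factor fixed before the data are seen.

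The cost is two form columns, a few table rows and one covariate, with some recall error in reported doses and about a minute more of patient and physician assistant time. None of it changes treatment.

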APPENDIX 2. CONVERSION FACTORS FOR COMMON OPIOID ANALGESICS TO ORAL MORPHINE EQUIVALENTS

Drug	Route	*Approximate Equianalgesic	**Morphine Equivalent
		Dose (mg)	Dose (MED) Factor
Codeine	Oral	200	0.15
Fentanyl	Parenteral	0.1	300
Hydrocodone	Oral	30	1.00
Hydromorphone	IM	1.5	20
Hydromorphone	Oral	7.5	4
Morphine	IM/IV	10	3
Morphine	Oral	30	1
Oxycodone	Oral	20	1.5
Oxymorphone	IM	1	30
Methadone	Oral	7.5	4

* Equivalent to 30 mg of oral morphine (Source: http://www.globalrph.com/narcotic.htm)

** 1mg of the drug converted to equivalent mg of oral morphine

APPENDIX 3. INCIDENCE OF OPIOID RELATED ADVERSE EVENTS

Instructions

Please indicate if you have experienced any of the following symptoms in the past 12 hours:

Symptom	Yes	No	Comments
Constipation			
Falling			
Нурохіа			
Lethargy			
Nausea			
Postoperative ileus			
Respiratory depression			
Sedation			
Somnolence			
Unsteadiness			
Urinary retention			
Vomiting

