Approved by the FDA in 2011, Exparel (liposomal bupivacaine) is a sustained-release version of the local anesthetic bupivacaine. While bupivacaine may last 6 to 12 hours to provide post-surgical relief, it is claimed that Exparel can last up to 72 hours after local infiltration at the surgical site [14]. Different studies have also compared the efficacy of Exparel to bupivacaine for the management of postsurgical pain following various surgical procedures, including inguinal hernia repair, breast augmentation, and TKA [15-20]. While some of these studies have supported the efficacy of Exparel to provide superior relief of postsurgical pain, others have found bupivacaine to be just as effective [20]. There is still however, a paucity of literature on the efficacy of Exparel for spine surgery pain management.

Study Questions/Objectives and Hypothesis

This study is aimed at prospectively examining clinical and economic outcomes when managing postsurgical pain using local infiltration of Exparel for patients undergoing primary, 1 or 2 level, lumbar laminectomy with or without fusion. There is a growing body of evidence suggesting that combining Exparel with a short acting numbing medicine gives much better pain coverage. The rationale is that Exparel can take several hours to have anesthetic onset and conventional thinking believes that if we can cover the immediate postoperative pain better with an immediate acting anesthetic to bridge the onset gap, then better outcomes will be achieved. The combination of these medications have been used in various studies previously in other areas of the body both in orthopedics and non-orthopedics and no adverse effects of combining these medications and in similar quantities/dosing have been observed [22,23,24]. To this end, we hypothesize that compared to patients that only received local infiltration of bupivacaine or only administered Exparel, the intervention group treated to a combination of Exparel and bupivacaine would, during their hospital stay following surgery, experience:

- 1. Reduced mean postoperative pain score (Wong-Baker pain faces scale of 0-no pain, to 10-extreme pain)
- 2. Reduced total consumption of opioids (in mean morphine equivalents)
- 3. Reduced overall cost of postoperative pain control medications
- 4. Decreased incidence of ORAEs

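### Opioid-related events are recorded only on a postoperative symptom checklist with no preoperative reading, so carried-over symptoms cannot be told apart from new ones and, if counted, dilute the arm difference

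*Combined protocol and SAP*

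**What the plan says.** The fourth hypothesis (Study Questions/Objectives and Hypothesis) is "Decreased incidence of ORAEs" in the combination arm. Study Methodology lists the secondary outcomes, ending with "mean LOS, and incidence of ORAEs", and describes how the data arise: "ORAEs will be documented using the checklist shown in Appendix 3 with assistance from a nurse during every nursing shift", that is, every 12 hours until discharge.

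Appendix 3 lists 12 symptoms with Yes, No and Comments columns under the instruction "Please indicate if you have experienced any of the following symptoms in the past 12 hours". It does not ask when a symptom began, whether it has changed since before surgery, or whether it is related to opioids. No preoperative completion is described, and no rule says how a Yes becomes an ORAE.

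On prior opioid use, the Background says that "many patients are already using opioids prior to their surgical procedure". The exclusion list in Study Methodology has one opioid-related item: "Prior treatment for alcohol, recreational drug, or opioid abuse". Appendix 1, under its exclusion heading, also asks: "Have you been taking opioid analgesics (also known as narcotics) such as Vicodin, Percocet, or OxyContin for more than 30 days". That item is absent from the exclusion list. Appendix 1 records pain medicines taken in the past month but none of the Appendix 3 symptoms.

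Proportions are to be compared by chi-square test. Logistic regression for confounding is mentioned, with no covariates named.

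**The concern.** Incidence means new events, but the form measures presence within a 12-hour window. A patient taking opioids before surgery may arrive with constipation, lethargy or nausea, and one with stenosis or radiculopathy may arrive unsteady. Each could answer Yes at the first postoperative shift whatever the assigned treatment. Depending on timing, the first look-back may even reach into the hours before surgery.

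Since nothing about these symptoms is collected beforehand, an analyst cannot later separate old from new. This is missing data collection, not just an unwritten analysis detail, and a reliable baseline cannot be recovered after the operation.

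At stake is the fourth hypothesis. Study Benefits to Virtua links part of the hoped-for saving to fewer ORAEs. If background symptoms enter the count, a true reduction in new events becomes harder to detect.

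**Working it through.** **The plan's own figure.** The only computed figure is the sample size for pain: 40 per group, 80% power, significance level 0.05, difference 1, variance 2. Take three means at -0.5, 0 and +0.5. The one-way ANOVA noncentrality with n = 40 is 40 × (0.25 + 0 + 0.25)/2 = 10, which gives power 80.5%, so 40 per group reproduces. With the planned enrolment of 45 per group, power is 85.2%. This figure concerns pain only and does not depend on the present point. The documents give no corresponding figure for ORAEs.

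**Inputs for ORAEs.**
- From Study Methodology: 45 per group, significance level 0.05, comparison of proportions.
- Assumed, because the documents are silent: a per-patient any-event endpoint; new-event rates of 50% in one arm and 25% in the other; two-sided pairwise testing.
- Also assumed: a share b of patients with a symptom present before surgery and again within a postoperative window. This share is taken as equal across arms and independent of the risk of a new event.

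**Dilution.** If carried-over symptoms are counted, the observed rate is b + (1 - b) × new-event rate. The difference between two arms is then (1 - b) × the true difference. Background that is equal across arms shrinks the contrast but does not reverse it.

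**Power.** By the normal approximation, with d the observed difference, p the mean of the two observed rates, and n = 45:
- SE0 = √[p(1 - p) × 2/n]
- SE1 = √[(p1(1 - p1) + p2(1 - p2))/n]
- power = Φ[(d - 1.96 × SE0)/SE1]

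For b = 0: p = 0.375, SE0 = 0.1021, SE1 = 0.0986, so Φ[(0.25 - 0.2000)/0.0986] = Φ(0.507) = 0.694.

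For b = 20%: p = 0.50, SE0 = 0.1054, SE1 = 0.1033, so Φ[(0.20 - 0.2066)/0.1033] = Φ(-0.064) = 0.475.

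| b | Observed rates | Difference | Pairwise power |
|---|---|---|---|
| 0 | 50.0% v 25.0% | 25.0 points | 69% |
| 10% | 55.0% v 32.5% | 22.5 points | 58% |
| 20% | 60.0% v 40.0% | 20.0 points | 47% |
| 30% | 65.0% v 47.5% | 17.5 points | 39% |
| 40% | 70.0% v 55.0% | 15.0 points | 31% |

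A three-arm chi-square test with one arm at the lower rate behaves alike: 70% at b = 0 and 40% at b = 30%. At b = 20% the risk ratio moves from 0.50 to 0.67, and the number per arm for 80% pairwise power rises from 58 to 97.

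**Sensitivity to the assumed rates.** From b = 0 to b = 30%, pairwise power falls from 54% to 26% for 40% v 20%, and from 83% to 54% for 60% v 30%. The direction is the same throughout; the size depends on the assumptions.

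**The case against.** Several objections have force.

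- **No counting rule.** A reader might infer that the plan counts every pre-existing symptom as an incident ORAE. The documents do not say so: they are silent on how a Yes becomes an event, the form has a Comments column, and a nurse assists. What stands is that the Comments column carries no instruction to record onset, so the information needed for any better rule is not reliably collected.
- **Who is enrolled.** If the Appendix 1 item on opioid use beyond 30 days is applied as an exclusion, many of the likeliest carriers of symptoms are not enrolled. Excluding cord compression and cauda equina syndrome limits carry-over further. This lowers b but does not make it nil, since shorter opioid use and other causes remain.
- **Unit of analysis.** The power figures need a per-patient any-event proportion, and the plan does not say whether incidence is per patient, per symptom or per shift. Analysed by symptom, carry-over would be nil for postoperative ileus and unlikely for hypoxia or respiratory depression.
- **Invented magnitudes.** Neither b nor the ORAE rates are in the documents. An intermittent symptom noted before surgery need not recur in a postoperative window, so b is smaller than the share with any preoperative symptom. Even at b = 0, illustrative power is only 69%, and the plan claims none for this outcome.
- **An imperfect remedy.** A rule of absent before, present after would discard worsening. In the extreme case where patients with a baseline symptom can never score, b = 30% gives 0.7 × 50% = 35% v 0.7 × 25% = 17.5%, and power 47%. That still exceeds the 39% without a baseline, but falls well short of 69%. It argues for counting worsened symptoms too.

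The recorded medication history and the planned logistic regression do not answer the point. Drug history is not a symptom baseline, and a model cannot adjust for a reading that was never taken.

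**Conclusion.** The point holds as one about data collection: the plan cannot distinguish carried-over from new symptoms when it tests the fourth hypothesis. If carried-over symptoms are counted, the absolute difference shrinks by the factor (1 - b). The illustrated loss of power, from 69% to between 58% and 39% for b of 10% to 30%, rests wholly on the assumed rates, the assumed per-patient endpoint, and carry-over that is equal across arms and independent of new-event risk. The actual size cannot be derived from the documents.

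Two stronger readings should be resisted. One is that the ORAE comparison is biased towards an arm; randomisation balances prior symptoms in expectation, so the effect is loss of contrast. The other is that the trial's main conclusion is endangered; this is one secondary outcome without a power claim, and the pain outcome and its sample size are untouched. It is a cheap improvement worth making before enrolment.

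**What to change.** 1. Complete Appendix 3 once before surgery, either with the Appendix 1 questionnaire or at admission on the day of surgery.
2. Add to the postoperative form a mark, for each symptom, showing whether it is new or worse than before surgery.
3. Define an incident ORAE, per patient, as a listed symptom that is new or has worsened from the preoperative reading, and state this as the unit for the chi-square comparison.
4. Report the all-symptom count as a sensitivity analysis.
5. Reconcile the exclusion list in Study Methodology with the Appendix 1 item on opioid use beyond 30 days, since expected carry-over depends on which applies.

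The cost is one extra completion of an existing 12-item form, one added mark per symptom, and one sentence of definition. Judging worsening brings some subjectivity. A preoperative reading does not remove symptoms caused by anaesthesia, so dilution is reduced, not eliminated.
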